### 7.2.2.1. **Treatment-Emergent Laboratory Abnormalities**

Treatment-emergent laboratory abnormalities are defined as values that increase at least 1 toxicity grade from baseline at any postbaseline time point, up to and including the date of last dose of study drug plus 30 days for subjects who permanently discontinued study drug.

If the relevant baseline laboratory value is missing, any abnormality of at least Grade 1 observed within the time frame specified above will be considered treatment emergent.

### 7.2.2.2. **Treatment-Emergent Marked Laboratory Abnormalities**

Treatment-emergent marked laboratory abnormalities are defined as values that increase at least 3 toxicity grades from baseline at any postbaseline time point, up to and including the date of the last dose of study drug plus 30 days for subjects who permanently discontinued study drug.

If the relevant baseline laboratory value is missing, any Grade 3 or 4 values observed within the timeframe specified above will be considered treatment-emergent marked abnormalities.

### 7.2.2.3. **Summaries of Laboratory Abnormalities**

Laboratory data that are categorical will be summarized using the number and percentage of subjects in the study with the given response at baseline and each scheduled postbaseline time point.

The following summaries (number and percentage of subjects) for treatment-emergent laboratory abnormalities will be provided by lab test and treatment group; subjects will be categorized according to the most severe postbaseline abnormality grade for a given laboratory test:

- Graded laboratory abnormalities
- Grade 3 or higher laboratory abnormalities
- Marked laboratory abnormalities

For all summaries of laboratory abnormalities, the denominator is the number of subjects with nonmissing postbaseline values up to 30 days after last dosing date.

A by-subject listing of treatment-emergent Grade 3 or 4 laboratory abnormalities will be provided by subject ID number and time point in chronological order. This listing will include all test results that were collected throughout the study for the lab test of interest, with all applicable severity grades displayed.

### 7.2.3. Liver-related Laboratory Evaluations

Liver-related abnormalities after initial study drug dosing will be examined and summarized using the number and percentage of subjects who were reported to have the following laboratory test values for postbaseline measurements:

- AST: (a)  $> 3$  times of upper limit of the normal range (ULN); (b)  $> 5 \times$  ULN; (c)  $> 10 \times$  ULN; (d)  $> 20 \times$  ULN
- ALT: (a)  $> 3 \times$  ULN; (b)  $> 5 \times$  ULN; (c)  $> 10 \times$  ULN; (d)  $> 20 \times$  ULN
- AST or ALT  $> 3 \times$  ULN and total bilirubin  $> 2 \times$  ULN

For individual laboratory tests, subjects will be counted once based on the most severe postbaseline values. For both the composite endpoint of AST or ALT and total bilirubin, subjects will be counted once when the criteria are met at the same postbaseline visit date. The denominator is the number of subjects in the Safety Analysis Set who have nonmissing postbaseline values of all relevant tests at the same postbaseline visit date. A listing of subjects who met at least 1 of the above criteria will be provided.

### 7.3. Body Weight, Height and Vital Signs

Descriptive statistics will be provided by treatment group for body weight, BMI and vital signs (resting blood pressure [systolic blood pressure and diastolic blood pressure], respiratory rate, pulse, and temperature) as follows:

- Baseline value
- Values at each postbaseline time point
- Change from baseline at each postbaseline time point

A baseline value will be defined as the last available value collected on or prior to the date/time of first dose of study drug. Change from baseline to a postbaseline visit will be defined as the postbaseline value minus the baseline value. Body weight and vital signs measured at unscheduled visits will be included for the baseline value selection.

In the case of multiple values in an analysis window, data will be selected for analysis as described in Section 3.7.3. No formal statistical testing is planned.

A by-subject listing of vital signs will be provided by subject ID number and time point in chronological order. Body weight, height, and BMI will be included in the vital signs listing, if space permits. If not, they will be provided separately.

Weight measured by the subjects at home from virtual visits due to COVID-19 impact will not be included in the vital signs summary, but they will be included in the listing with a flag to indicate which records were collected at home.

## **7.4. Prior and Concomitant Medications**

Medications reported at screening and during the study will be coded using the current version of the World Health Organization (WHO) Drug dictionary.

### **7.4.1. Prior Medications**

Prior medications are defined as any medications taken before a subject took the first dose of study drug at baseline.

General prior and CD-specific prior medication will be summarized separately by preferred name using the number and percentage of subjects for each treatment group and overall. A subject reporting the same medication more than once will be counted only once when calculating the number and percentage of subjects who received that medication. The summary will be ordered by preferred term in descending overall frequency. For drugs with the same frequency, sorting will be done alphabetically.

For the purposes of analysis, any medication with a start date prior to the first dosing date of study drug will be included in the prior medication summary regardless of when the stop date is. If a partial start date is entered the medication will be considered prior unless the month and year (if day is missing) or year (if day and month are missing) of the start date are after the first dosing date. Medications with a completely missing start date will be included in the prior medication summary, unless otherwise specified.

Summaries will be based on the Safety Analysis Set. No formal statistical testing is planned.

### **7.4.2. Concomitant Medications**

Concomitant medications are defined as medications taken while a subject took study drug. General and CD-specific concomitant medications will be summarized, separately, by preferred name using the number and percentage of subjects for each treatment group. A subject reporting the same medication more than once will be counted only once when calculating the number and percentage of subjects who received that medication. The summary will be ordered by preferred term in descending overall frequency. For drugs with the same frequency, sorting will be done alphabetically.

For the purposes of analysis, any medication with a start date prior to or on the first dosing date of study drug and continued to take after the first dosing date, or started after the first dosing date but prior to or on the last dosing date of study drug will be considered concomitant medications. Medications started and stopped on the same day as the first dosing date or the last dosing date of study drug will also be considered concomitant. Medications with a stop date prior to the date of first dosing date of study drug or a start date after the last dosing date of study drug will be excluded from the concomitant medication summary. If a partial stop date is entered, any medication with the month and year (if day is missing) or year (if day and month are missing) prior to the date of first study drug administration will be excluded from the concomitant medication summary. If a partial start date is entered, any medication with the month and year (if

day is missing) or year (if day and month are missing) after the study drug stop date will be excluded from the concomitant medication summary. Medications with completely missing start and stop dates will be included in the concomitant medication summary, unless otherwise specified. Summaries will be based on the Safety Analysis Set. No formal statistical testing is planned.

All prior and concomitant medications (other than per-protocol study drugs) will be provided in a by-subject listing sorted by subject ID number and administration date in chronological order.

#### **7.5.                   Electrocardiogram Results**

A shift table of the investigators' assessment of ECG results at each visit compared with baseline values will be presented by treatment group using the following categories: normal; abnormal, not clinically significant; abnormal, clinically significant. The number and percentage of subjects in each cross-classification group of the shift table will be presented. Subjects with a missing value at baseline or postbaseline will not be included in the denominator for percentage calculation. No formal statistical testing is planned.

A by-subject listing for ECG assessment results will be provided by subject ID number and time point in chronological order.

#### **7.6.                   Other Safety Measures**

A data listing will be provided for subjects who become pregnant during the study.

#### **7.7.                   Changes from Protocol-Specified Safety Analyses**

There are no deviations from the protocol-specified safety analyses.

10

CCD

1

1

1

1

1

CCII

## **11. SOFTWARE**

SAS® Software Version 9.4 (SAS Institute Inc., Cary, NC, USA) is to be used for all programming of tables, listings, and figures.

## 12. SAP REVISION

Revision Date (DD MMM YYYY)	Section	Summary of Revision	Reason for Revision
Original Version (05 NOV 2019)			
Version 2 (01 March 2021)	3.5.1	Added missing data imputation rule for MRI data, laboratory data and vital signs data	To clarify missing data imputation rule for analysis
	3.7.2	Updated analysis visit window length for Week 18 and Week 24	To map data to analysis visits based on more clinical relevant rationale
	3.8, 4, 7.2, 7.3	Added assessment of COVID-19 impact	To better understand the COVID-19 impact on subject disposition and missing data
	5	Modified the list of variables to be summarized in baseline characteristic tables	To provide better characterization of the investigated patient populations
	██████████ CCI ██████████	██████████	██████████
	7.1.7	Added adverse event of interest for MACE, ASTE, and VTE based on positively adjudicated events by the cardiovascular safety endpoint adjudication committee	To better address safety concerns
	7.2.4	Removed shift table summaries	The shift table summaries are less useful to detect safety signal given small sample size in this study. The shift table summaries will be included in integrated safety analysis if needed
	Appendix 3	Added a list of biologics for CD treatment	To clarify biologics considered as general CD treatment
	Appendix	Deleted the list of preferred terms for each category of adverse events of interest (Version 1 Appendix 11 to 16)	To reduce the burden to keep track of the list of preferred terms due to MedDRA up-versioning. The lists will be provided in the CSR.
	Global	Administrative and editorial changes have been made throughout the SAP, where appropriate	Improve clarity and consistency

## Appendix 1. Schedule of Assessments

Period	Screening	Treatment										Follow-Up	
		1	2	3	4	5	6	7	8	9	10	PTx a	ET
Visit													
Week		0	2	4	6	10	14	18	20	24			
Study Day	-30 to -1	1	15	29	43	71	99	127	141	169			
Visit Window (±)			±3	±3	±3	±2	±3	±3	±5	±5	±3		
Written Informed Consent	X												
Medical History & Demographics	X												
Crohn's Disease & Treatment History	X												
12-lead ECG	X						X						X b
Review of Inclusion/Exclusion Criteria	X	X											
Physical Exam (Complete including perianal) c	X												
Physical Exam (symptom-based) and perianal assessment c		X	X	X	X	X	X	X		X	X	X	
Vital Signs	X	X	X	X	X	X	X	X		X	X	X	
Weight	X	X	X	X	X	X	X	X		X	X	X	
Height	X												
Adverse Events	X	X	X	X	X	X	X	X		X	X	X	
Concomitant Medications	X	X	X	X	X	X	X	X		X	X	X	

Period	Screening	Treatment										Follow-Up	
		1	2	3	4	5	6	7	8	9	10	PTx a	ET
Visit													
Week		0	2	4	6	10	14	18	20	24			
Study Day	-30 to -1	1	15	29	43	71	99	127	141	169			
Visit Window (±)			±3	±3	±3	±2	±3	±3	±5	±5	±3		
Randomization		X											
Study Drug Dispensing		X		X		X	X	X					
CCI													
eDiary instruction & review e	X	X	X	X	X	X	X	X		X			
Flexible Sigmoidoscopy o	X									X		X r	
MRI f	X									X		X s	
Stool for C. diff toxin, pathogenic E. coli , Salmonella , Shigella , Campylobacter and Yersinia testing		X											
Stool O&P	X												
CCI													
CCI													

Period	Screening	Treatment										Follow-Up	
		1	2	3	4	5	6	7	8	9	10	PTx a	ET
Visit	1												
Week		0	2	4	6	10	14	18	20	24			
Study Day	-30 to -1	1	15	29	43	71	99	127	141	169			
Visit Window (±)			±3	±3	±3	±2	±3	±3	±5	±5	±3		
Urine drug screen g	X												
Urinalysis q	X										X		
Pregnancy Test h	X	X		X	X	X	X	X	X	X	X	X	X
TB screening i	X												
Chest x-ray q	X												
HBV, HCV, HIV screening j	X												
Hematology	X	X	X	X	X	X	X	X			X	X	X
Chemistry	X	X	X	X	X	X	X	X			X	X	X
Fasting Lipids p		X				X					X		
CRP	X	X	X	X	X	X	X	X			X	X	X
Blood TCR/BCR repertoire sample k		X		X		X					X		
CCI													
CCI													
Blood transcriptome sample		X		X		X					X		
CCI													
Serum immunoglobulin		X		X		X					X	X	X

Period	Screening	Treatment										Follow-Up	
		1	2	3	4	5	6	7	8	9	10	PTx a	ET
Visit													
Week		0	2	4	6	10	14	18	20	24			
Study Day	-30 to -1	1	15	29	43	71	99	127	141	169			
Visit Window (±)			±3	±3	±3	±2	±3	±3	±5	±5	±3		
CCI													
CCI													
CCI													

a The Post-Treatment (PTx) visit should occur 30 days after the last dose of study drug. Only subjects who roll over into the LTE study will not complete PTx assessments.

b For subjects who terminate prior to Week 10

c A complete physical examination (PE) including; vital signs, body weight, height, and perianal assessment (including completion of the Perianal Fistula Assessment Worksheet) will be performed at screening. A symptom-directed PE and perianal assessment(including completion of the Perianal Fistula Assessment Worksheet) should be performed at all other time points.

e Subjects should begin filling out the eDiary the day of their initial screening visit and continue to fill it out throughout the remainder of the study.

f Refer to Section 6.6 of study protocol for details on the MRI procedure

g Positive cocaine test disqualifies subject; positive amphetamines, barbiturates, benzodiazepines, and opioids require medical monitor review

h All females meeting the childbearing potential criteria must have a serum pregnancy testing at screening and a urine pregnancy test must be completed every 4 weeks at a minimum. If any pregnancy test is positive, study drug must be immediately interrupted and the subject should come to the site for serum pregnancy test in clinic.

i Proof of no active or untreated latent TB at screening. Subjects who are diagnosed with latent TB at screening must initiate an adequate course of prophylaxis as per local standard of care, for a minimum of 4 weeks prior to randomization. Subject may initiate study drug dosing only after consultation with the Study Medical Monitor.

j An HIV-1/HIV-2 antibody test, a HCV antibody test, a HBV surface antigen test, a HBV surface antibody test, and a HBV core antibody test will be performed on all subjects; subjects with any positivity will be excluded unless the Hepatitis B surface antibody is the sole positive result (indicating immunization)

k TCR: T-cell receptor; BCR: B-cell receptor

o Refer to Section 6.5 of study protocol for details on the flexible sigmoidoscopy procedure

p Subjects should fast (no food or drinks, except water) for at least 8 hours prior to blood sample collection at Day 1, Week 10, and Week 24

q Chest x-ray (views as per local guidelines) taken at screening or within the 3 months prior to screening (with the report or films available for investigator review) without evidence of active or latent TB infection

r Subjects meeting non-response or disease worsening criteria should undergo a flexible sigmoidoscopy assessment prior to exiting the study.

s Subjects meeting non-response or disease worsening criteria should undergo a pelvic MRI prior to exiting the study.

## **Appendix 2. List of Biologics for Perianal Fistulizing CD Treatment**

The drug names of biologics considered as treatment for perianal fistulizing CD are listed below.

No.	Drug Class	Drug Name
1	TNF $\alpha$ antagonist	Adalimumab
2	TNF $\alpha$ antagonist	Certolizumab/Certolizumab Pegol
3	TNF $\alpha$ antagonist	Infliximab
4	TNF $\alpha$ antagonist	TNF $\alpha$ antagonist biosimilar (to adalimumab, Certolizumab/Certolizumab Pegol, or infliximab)

[figure not shown]

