3.3. Study Treatments

Based on protocol eligibility criteria, subjects will be screened for enrollment and randomized into 1 of 3 treatment groups in a blinded fashion in a 2:2:1 ratio as follows:

Treatment group 1 (n = 30): filgotinib 200 mg and PTM filgotinib 100 mg, once daily

Treatment group 2 (n = 30): filgotinib 100 mg and PTM filgotinib 200 mg, once daily

Treatment group 3 (n = 15): PTM filgotinib 200 mg and PTM filgotinib 100 mg, once daily

Note: US males who are not dual refractory will be randomized in a 2:1 ratio to either filgotinib 100 mg or matching placebo. For the purposes of this protocol, US males who have failed at least one prior TNF antagonist AND either previously failed vedolizumab induction therapy or are concomitantly taking vedolizumab at Day 1 and present with actively draining perianal fistulae despite continued vedolizumab therapy will be considered as dual refractory patients. This assessment is based on recently published data from a subgroup analysis of the GEMINI-2 study, showing a beneficial effect of vedolizumab treatment for patients that were randomized with actively draining perianal fistulae at baseline (Feagan 2018).

Treatment assignments will be stratified according to the following factors:

- Anatomy of draining perianal fistulae at screening determined by MRI (simple *versus* complex)
- Receiving vedolizumab therapy concomitantly at Day 1 (Yes or No)
- Presence of moderately to severely active proctitis (Yes or No)

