3.5.2. Study Drug Discontinuation Considerations

The Study Medical Monitor should be consulted prior to study drug discontinuation when medically feasible.

Study drug must be permanently discontinued in the following instances:

- Any opportunistic infection
- Any **serious** infection that requires antimicrobial therapy or hospitalization, or any infection that meets SAE reporting criteria.
- Febrile neutropenia (temperature $> 38.3^{\circ}\text{C}$ or a sustained temperature of $> 38^{\circ}\text{C}$ for more than one hour) with absolute neutrophil count of $< 1,000/\text{mm}^3$

- Symptomatic anemia (eg, signs/symptoms including pallor, shortness of breath, new heart murmur, palpitations, lethargy, fatigue) with hemoglobin < 7.5 g/dL, or if transfusion is indicated regardless of hemoglobin value
- Complicated herpes zoster infection (with multi-dermatomal, disseminated, ophthalmic, or CNS involvement)
- Evidence of active Hepatitis C Virus (HCV) during the study, as evidenced by HCV RNA positivity
- Evidence of active Hepatitis B Virus (HBV) during the study, as evidenced by HBV DNA positivity
- Any thromboembolic event that meets SAE reporting criteria
- Unacceptable toxicity, or toxicity that, in the judgment of the investigator, compromises the subject's ability to continue study-specific procedures or is considered to not be in the subject's best interest
- Subject request to discontinue for any reason
- Subject noncompliance
- Pregnancy during the study; refer to Section [7.7.2.1](#)
- Discontinuation of the study at the request of Gilead, a regulatory agency or an institutional review board or independent ethics committee (IRB/IEC)
- Subject use of prohibited concurrent therapy may trigger study drug discontinuation; consultation should be made with the Study Medical Monitor.
- Laboratory Criteria: After becoming aware of any of the below described abnormal laboratory changes occurring at any one time, an unscheduled visit (ie, sequential visit) should occur to retest within 3 to 7 days (except creatinine, which should be retested 7 to 14 days apart).
 - Two sequential neutrophil counts < 750 neutrophils/mm³ (SI: < 0.75x10⁹ cells/L)
 - Two sequential platelet counts < 75,000 platelets/mm³ (SI: < 75.0x10⁹ cells/L)

Two sequential aspartate aminotransferase (AST) or alanine aminotransferase (ALT) elevations > 3 times the upper limit of normal range (x ULN) and at least one of the following confirmed values:

- total bilirubin > 2 x ULN

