## **III. Potentially effective biologic agent use**

**Commencement of a biologic agent** including but not limited to TNF $\alpha$  antagonists, IL-12/23 antagonists, and vedolizumab (or similar agents), regardless of indication for use and duration ([Appendix 3](#)).

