## **III. Potentially effective biologic agent use**

**Commencement of a biologic agent** including TNF $\alpha$  antagonists, regardless of indication for use and duration ([Appendix 2](#)).

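### The fistula treatment-failure rule covers only TNFα antagonists, so a subject who newly starts vedolizumab on study can still count as a primary-endpoint responder

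*SAP*

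**What the plan says.** SAP Appendix 11 applies to combined fistula response and combined fistula remission at Week 24 and to the times to clinical fistula response and remission. Once a subject meets a failure criterion, later efficacy data are set to missing. If too little remains to determine a binary endpoint, the subject is a non-responder.

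Part III of that appendix makes starting a biologic a failure. The only class it names is TNFα "antagonists, regardless of indication for use and duration", and it refers to Appendix 2 for the drugs. Appendix 2 opens with "The drug names of biologics considered as treatment for perianal fistulizing CD are listed below" and lists adalimumab, certolizumab, infliximab and their biosimilars.

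The parallel rule for luminal endpoints, Appendix 10 III, is wider. It is worded as open-ended, covers TNFα "antagonists, IL-12/23 antagonists, and vedolizumab (or similar agents), regardless of indication for use and duration", and refers to Appendix 3, which adds natalizumab, vedolizumab and ustekinumab. Proctitis remission falls under this rule.

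Protocol Section 3.3, repeated in SAP Section 1.2, rests the dual-refractory definition for US males on published data "showing a beneficial effect of vedolizumab treatment for patients that were randomized with actively draining perianal fistulae at baseline".

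**The concern.** The plan relies on a vedolizumab effect on draining fistulae when it decides which US males may be allocated to 200 mg, but not when it decides whether a fistula closure belongs to study treatment. If a subject starts vedolizumab on study and the fistula then closes, the closure is credited to the randomised arm. A subject with active proctitis at baseline would be a failure for proctitis remission and could be a responder for the primary endpoint because of the same drug start.

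There is no hypothesis test, so the point estimates and their 90% intervals are the result. New therapy after randomisation is more likely in subjects who are doing badly, so an imbalance between arms is plausible. More such starts on placebo would shrink the filgotinib-minus-placebo difference; more on filgotinib would inflate it.

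**Working it through.** **Step 1: does any other visible rule catch the case?**

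- *Prohibited therapy.* Protocol Section 3.5.2 says "Subject use of prohibited concurrent therapy may trigger study drug discontinuation", so discontinuation is possible but not automatic. Where worsening Crohn's disease needs a prohibited drug, Section 3.8 leaves discontinuation to the investigator's discretion.
- *Table 5-1.* Ustekinumab and natalizumab are prohibited through the end of study. Vedolizumab is not named. The row for other biologics asks for medical monitor consultation.
- *Allowed use.* Section 5.4.1 permits vedolizumab only if stable for 14 weeks before randomisation. A new start is outside permitted use, but no analysis consequence is attached.
- *Non-responder imputation (SAP Section 6.1).* It applies to binary endpoints when measurements are insufficient. A subject with a Week 24 examination and MRI has sufficient measurements.
- *Time-to-event endpoints (SAP Table 6-1).* The first observed closure is an event. Only an Appendix 11 failure removes later data.

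So in the visible text the gap is open. Some efficacy text is redacted, and this conclusion cannot extend to it.

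**Step 2: the plan's own figures.** SAP Table 1-1 gives exact 90% intervals for n = 30. With lower limit = Beta quantile(0.05; x, n − x + 1) and upper limit = Beta quantile(0.95; x + 1, n − x), all seven rows reproduce. For example, 15/30 gives 33.89% to 66.11%, printed as 34% to 66%. No stated figure is wrong; the issue is a definition.

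**Step 3: size per subject.** Allocation of 75 at 2:2:1 gives 30, 30 and 15. One subject reclassified from responder to failure moves placebo by 1/15 = 6.7 points and a filgotinib arm by 1/30 = 3.3 points.

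**Step 4: illustration.** The documents give no rate of on-study starts, so the number reclassified is an assumption (0 to 2 per arm), as are the starting counts of 15/30 filgotinib and 4/15 placebo responders. The SAP names no interval method for the difference. An unpooled Wald 90% interval is used here: d ± 1.645 × √[p₁(1 − p₁)/n₁ + p₀(1 − p₀)/n₀]. For the first row: √(0.5 × 0.5/30 + 0.267 × 0.733/15) = 0.146, and 1.645 × 0.146 = 0.240.

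| Reclassified, placebo / filgotinib | Counts | Difference (points) | 90% CI |
|---|---|---|---|
| 0 / 0 | 15/30 vs 4/15 | 23.3 | −0.7 to 47.4 |
| 1 / 0 | 15/30 vs 3/15 | 30.0 | 7.3 to 52.7 |
| 2 / 0 | 15/30 vs 2/15 | 36.7 | 15.8 to 57.5 |
| 0 / 1 | 14/30 vs 4/15 | 20.0 | −4.0 to 44.0 |
| 0 / 2 | 13/30 vs 4/15 | 16.7 | −7.3 to 40.6 |
| 1 / 2 | 13/30 vs 3/15 | 23.3 | 0.7 to 45.9 |

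One or two subjects can shift the estimate by 3 to 13 points either way, and equal shifts in the two arms cancel, as in the last row.

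**The case against.** The narrow list looks like a choice, not a slip. Inclusion criterion 8 names three qualifying classes: antibiotics, immunomodulators and TNFα antagonists. SAP Section 5.2 uses the same three for fistula treatment history and puts vedolizumab and ustekinumab under other Crohn's treatment. Appendix 11 follows the same division, and the SAP revision table says Appendix 3 was added for general Crohn's treatment. Protocol Section 1.1 says that, of the biologics it discusses, only infliximab had been shown effective for fistulizing disease in a randomised trial. That explains where the list came from but does not justify it as a failure rule. Appendix 2 also holds adalimumab and certolizumab, and Appendix 11 counts new antibiotics and immunomodulators as potentially effective. By the plan's own citation, vedolizumab meets that standard.

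The gap is also narrow, and this part stands. It needs a start outside permitted use, continued participation, Week 24 clinical and MRI data, and a response. Week 10 non-responders and subjects meeting the later worsening criteria must leave blinded treatment, and many would then be non-responders by imputation.

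A reader might go further and infer that the trial stratifies on "Receiving vedolizumab therapy concomitantly at Day 1 (Yes or No") because vedolizumab helps fistulae. The documents do not say so. The cited evidence is attached to the dual-refractory definition, no reason is given for the stratification factor, and SAP Section 1.2 applies that factor only after amendment 4, with prior TNFα antagonist exposure used before. Nor does inclusion criterion 13e show fistula activity: it allows vedolizumab for luminal disease, and similar stability rules cover 5-ASA and steroids. The washout in exclusion criterion 23 is general to biologics.

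Finally, the wording of Appendix 11 III could be read as non-exhaustive. The pointer to Appendix 2 and the contrast with Appendix 10 favour the narrow reading. If the wider one was meant, the text and its pointer disagree and the primary endpoint could be programmed two ways.

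**Conclusion.** The concern holds in a limited form. As the visible text reads, a subject who newly starts vedolizumab, ustekinumab or natalizumab and has Week 24 fistula and MRI data can be a responder for the primary endpoint. For vedolizumab this conflicts with a fistula benefit that the plan itself cites. For ustekinumab and natalizumab the argument is weaker: they are prohibited and Appendix 10 III with Appendix 3 counts them, but no fistula benefit is cited for ustekinumab.

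The size is 6.7 points per placebo subject and 3.3 points per filgotinib subject. The number affected is not given and may be zero. It would be wrong to conclude that the result is biased by a known amount or in a known direction. This is a should-fix item: possible bias in a small descriptive trial, removable at almost no cost.

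**What to change.** In SAP Appendix 11 III, replace the reference to Appendix 2 with one to Appendix 3, so that starting any listed biologic after the first dose is a fistula treatment failure for analysis. State that vedolizumab ongoing at Day 1 is not a start. Treat the list as closed and do not import the open-ended wording of Appendix 10 III. Combined with the phrase that disregards indication, that wording would also capture unrelated biologics, such as denosumab, that the medical monitor may allow. If the list is closed, golimumab needs adding to it by name, because protocol Table 5-1 names it and neither appendix does.

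Keep Appendix 2 for the treatment-history table. Report the TNFα-only rule as a sensitivity analysis, with the number of subjects per arm whose classification differs.

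The change is a sentence or two, best made before unblinding, and uses concomitant medication data already collected. If made after SAP finalization, it should be documented in the study report, as SAP Section 1 requires. The cost is that response rates may be slightly lower.
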